8.1.1 Ocular Adverse Events

The following ocular events will be considered AEs for the purposes of this study:

- Decrease in BCVA of at least ≥ 15 letters or ≥ 3 lines from the previous BCVA measurement
- Moderate or severe (Grade 3 or 4) ocular findings compared to the last ocular examination
- Worsening of >2 steps in anterior chamber cell count or vitreous haze compared to the last ocular examination
- Increase in IOP of >10 mmHg at two visits at least 1 week apart or an increase in IOP to >25 mmHg

8.1.2 Serious Adverse Events

An SAE is any AE that results in one of the following outcomes:

- Death/Fatal
- Is life-threatening (the term “life-threatening” refers to an event in which the subject was at risk of death at the time of the event; it does not refer to an event which hypothetically might have caused death if it were more intense).
- Requires in-patient hospitalization (formal admission to a hospital for medical reasons for any length of time), or prolongs existing hospitalization.
- Results in a persistent or significant disability/incapacity, or substantial disruption of the ability to conduct normal life functions.
- Congenital anomaly/birth defect (in the child of a subject who was exposed to the study treatment).
- Other important medical event. Medical and scientific judgment should be exercised in determining whether an event is an important medical event. An important medical event may not be immediately life-threatening and/or result in death or hospitalization but required medical intervention in order to prevent a SAE outcome. However, if it is determined that the event may jeopardize the subject and/or may require intervention to prevent one of the other SAE outcomes, the important medical event should be reported as serious. Examples of such events are intensive treatment in an emergency room or at home for allergic bronchospasm; blood dyscrasias or convulsions that do not result in hospitalization; or development of drug dependency or drug abuse.

The following hospitalizations will not be considered SAEs:

- A visit to the emergency room or other hospital department for <24 hours that does not result in in-patient admission (unless considered an “important medical event” or a “life-threatening event”).
- Elective surgery or planned surgery prior to signing the ICF.
- Admissions as per protocol for a planned medical/surgical procedure.

- Routine health assessments requiring admission for baseline/trending of health status (eg, routine colonoscopy).
- Medical/surgical admission for a purpose other for healthcare purposes and was planned prior to entry into the study (appropriate documentation is required in these cases).
- Admission encountered for another life circumstance that carries no bearing on health status and/or requires no medical/surgical intervention (eg, lack of housing, economic inadequacy, care-giver respite, family circumstances, administrative).

Clarification of SAEs:

- Death is an outcome of an AE, and not an AE in itself.
- All deaths, regardless of cause or relationship, must be reported.
- Complications that occur during hospitalizations are AEs. If a complication prolongs hospitalization, it is an SAE.
- “In-patient hospitalization” means the subject has been formally admitted to a hospital for medical reasons for any length of time. This may or may not be overnight. It does not include presentation to, and/or care within, an emergency department.
- The Investigator should attempt to establish a diagnosis of the event based on signs, symptoms, and/or other clinical information.

8.1.3 Sight-Threatening Ocular Events Defined as SAEs in This Study

In addition to the standard SAE categories described above, this study defines these additional ocular events as SAEs:

- An AE that causes a decrease in visual acuity of ≥ 30 letters or ≥ 6 lines from the most recent previous measurement of visual acuity, lasting more than 1 hour.
- An AE that causes a decrease in visual acuity to light perception or worse, lasting more than 1 hour.
- An AE that requires surgical intervention (eg, conventional surgery, vitreous tap or biopsy with intravitreal injection of anti-infectives, or laser or retinal cryopexy with gas) to prevent permanent loss of sight.
- An AE that is associated with severe intraocular inflammation (ie, 4.0 anterior chamber cell score, 4+ flare or 4+ vitritis).
- Two consecutive IOP measurements of 30 mmHg or higher taken at least 72 hours apart when a subject is already being treated with two IOP-lowering medications.
- An IOP < 6 mmHg requiring medical intervention.
- An AE that in the opinion of the Investigator requires medical or surgical intervention to prevent permanent loss of sight.

The Investigator must employ all necessary therapeutic measures to resolve the SAE. Any medications or therapies used to treat the SAE must be recorded in the eCRF.

8.1.4 Clinical Laboratory Adverse Events

An abnormal laboratory result should be considered an AE if it:

- Results in the initiation or change of an intervention (eg, increased dose of medication), based on medical evaluation (eg, packed red cells for low hemoglobin).
- Results in any out of range laboratory value that in the Investigator's judgment fulfills the definitions of an AE.
- Increases in severity compared to baseline.

Abnormal laboratory values should not be listed as separate AEs if they are considered to be part of the clinical syndrome that is being reported as an AE. Any laboratory abnormality considered to constitute an AE should be reported on the AE eCRF. It is the responsibility of the Investigator to review all laboratory findings in all subjects and determine if they constitute an AE. Medical and scientific judgment should be exercised in deciding whether an isolated laboratory abnormality should be classified as an AE.

All laboratory AEs should be repeated and reassessed by the Investigator to track resolution and especially to confirm if they meet the definition of serious. If serious, they will be reported as SAEs.

The Investigator or a licensed designee must review all laboratory results in a timely manner as demonstrated by signature/date.

8.1.5 Adverse Event Severity and Relationship

Adverse event severity is defined as a qualitative assessment of the intensity of an AE as determined by the Investigator. The assessment of severity is made irrespective of the relationship or seriousness of the event to study treatment or the injection device.

In the absence of an assigned severity per the CTCAE v5.0 ([Appendix 4](#)) grading criteria, the Investigator will grade AEs according to the following severity criteria:

Mild/Grade 1: The event may be noticeable to subject; does not influence daily activities; usually does not require intervention.

Moderate/Grade 2: The event may be of sufficient severity to make subject uncomfortable; performance of daily activities may be influenced; intervention may be needed.

Severe/Grade 3: The event may cause severe discomfort; usually interferes with daily activities; subject may not be able to continue in the study; treatment or other intervention usually required.

Life- or Sight-Threatening/Grade 4: The event requires urgent intervention to preserve life and/or permanent loss of vision.

Death/Grade 5: The event resulted in the subject's death.

The relationship of study treatment (ie, Yutiq 0.05 mg), the injector, or the injection procedure, to each AE must be determined by the Investigator according to the following:

Not Related:	Evidence indicates no plausible direct relationship to the study treatment, device, or procedure, or there is a reasonable causal relationship between non-investigational product, concurrent disease, or circumstance and the AE; and/or a causal relationship is considered biologically implausible.
Possibly Related:	There is reasonable causal relationship between the study treatment, device, or procedure and the AE. There may or may not be a clinically-plausible temporal sequence between the onset of the AE and study treatment, device, or procedure; the AE is not reasonably supported by other conditions.
Probably Related:	The study medication, device, or procedure and AE occurrence are reasonably related in time; a clinically-plausible temporal sequence between the onset of the AE and study treatment, device, or procedure is likely; based upon the Investigator's clinical experience, the association of the AE with study medication, device, or procedure is likely; all other potential causes have been ruled out.

If the relationship between the AE/SAE and the sequence study treatment, device, or procedure is determined to be "possible" or "probable", the event will be considered related for the purposes of expedited regulatory reporting.

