1.2 Uveitis

Uveitis is defined as inflammation of the uveal tract (iris, ciliary body, choroids) or adjacent structures of the eye. The cause of an inflammatory reaction in the inner eye can be infectious, traumatic, neoplastic, or autoimmune. According to the classification scheme recommended by the International Uveitis Study Group, the disease can be classified on the basis of anatomic locations: anterior, intermediate, posterior, or panuveitis.

Uveitis affecting the posterior segment of the eye is responsible for approximately 10% of blindness in the US. Chronic non-infectious uveitis affecting the posterior segment of the eye can occur at any age and affects people of different ethnic origins. The inflammation that affects the choroid and retina may be a primary intraocular process or an ocular manifestation of systemic disease. Uveitis of the posterior segment accounts for most of the loss of vision in patients with uveitis due to cystoid macular edema, glaucoma, retinal detachment, subretinal fibrosis, cataract, and optic disk atrophy.

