1.3 Current Treatments for Uveitis

Uveitis is often a chronic disease requiring long-term medical therapy. Currently, medical management of uveitis of the posterior segment includes the local administration of corticosteroid (topical, periocular, intravitreal) and/or systemic steroids or immunosuppressants. Immunosuppressive therapy is used for patients with severe uveitis who cannot tolerate or do not respond to systemic corticosteroid therapy. The goal of therapy is to suppress the inflammation in the back of the eye.

There are disadvantages associated with these treatments and/or their routes of administration. All corticosteroid therapy, including systemic, is associated with ocular side effects, in particular cataract and corticosteroid-induced increased intraocular pressure (IOP), but these side effects are more commonly seen with local therapy. Topical delivery is not effective for the treatment of uveitis of the posterior segment due to its limited intraocular penetration. Periocular or intravitreal corticosteroid injections may be required frequently; however, injections have additional potential risks such as globe perforation, orbital fibrosis, endophthalmitis, and ptosis.

In addition to Yutiq[®], corticosteroids currently approved for the intravitreal treatment of chronic non-infectious uveitis affecting the posterior segment of the eye include Retisert[®] (invented by EyePoint and licensed to Bausch and Lomb), OZURDEX[®], and TRIVARIS[®]. Despite the availability of these approved products as intravitreal therapy of uveitis of the posterior segment, systemic corticosteroids remain the mainstay of uveitis therapy ([MUST Group 2011](#)). However, long-term use of systemic corticosteroids is associated with significant side effects ([Brunton et al. 2006](#)) and may not be a practical option for many patients.

Yutiq 0.05 mg, a product that is relatively simple to administer and delivers the corticosteroid locally for at least 6 months, may offer significant benefits over existing local and systemic steroid therapies in the treatment of chronic non-infectious uveitis affecting the posterior segment of the eye.

For more complete information regarding the safety profile and efficacy of Yutiq 0.05 mg, please refer to the current Yutiq Investigator's Brochure (IB).

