8.1 Adverse Events

The following are specific definitions of terms guided by the International Conference on Harmonization (ICH E2) Guidelines for Good Clinical Practice (GCP) and the US Code of Federal Regulations (CFR) that apply to the following sections. The severity of AEs will be graded by the Common Terminology Criteria for Adverse Events (CTCAE), version 5 ([Appendix 4](#)).

Definition of Adverse Event:

An AE is defined as any new untoward medical occurrence or worsening of a pre-existing medical condition in a patient or clinical investigation subject administered an investigational (medicinal) product and that does not necessarily have a causal relationship with the product. An AE can therefore be any unfavorable and unintended sign (including an abnormal laboratory finding, for example), symptom, or disease temporally associated with the use of an investigational product, whether or not considered related to the investigational product.

AEs may also include pre- or post-treatment complications that occur as a result of protocol-specified procedures (eg, invasive procedures such as venipuncture, delivery procedure, etc). Pre-existing conditions that increase in severity or change in nature during (or as a consequence of use of a medicinal product in) the study will also be considered AEs.

An AE Will Not Include:

- Medical or surgical procedures (eg, surgery, endoscopy, tooth extraction, transfusion) for events that led to the procedure
- Pre-existing diseases, conditions, or laboratory abnormalities present or detected prior to the Screening visit, unless they worsen during the study
- Situations where an AE or untoward medical occurrence has not occurred (eg, hospitalization for elective surgery, social and/or convenience admissions)

Associated with the Use of the Drug (Causality):

There is a reasonable possibility that the event may have been caused by the investigational drug (and/or the administration procedure).

Unexpected Adverse Event:

Any event that is not identified in nature, severity, or frequency in the current version of the IB. For example, if the IB referred to elevated hepatic enzymes or hepatitis, then an event of hepatic necrosis would be considered unexpected by the virtue of the greater severity. The Sponsor or designee will determine AE expectedness.

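### Protocol 8.1.5 forces an adverse event with both a reasonable treatment link and a reasonable alternative cause into Not Related, in conflict with the causality definition in 8.1

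*Protocol*

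**What the plan says.** Protocol 8.1 states when an event counts as associated with the drug: "There is a reasonable possibility that the event may have been caused by the investigational drug (and/or the administration procedure"). It makes no exception for events that might also have another cause.

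Protocol 8.1.5 then gives the scale by which the relationship "must be determined by the Investigator according to the following":

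- *Not Related* has several limbs. One, joined by *or*, is that "there is a reasonable causal relationship between non-investigational product, concurrent disease, or circumstance and the AE".
- *Possibly Related* needs a reasonable link to treatment, device or procedure, and ends with the condition that "the AE is not reasonably supported by other conditions".
- *Probably Related* ends with the condition that "all other potential causes have been ruled out".

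The same section says that where the relationship is possible or probable, "the event will be considered related for the purposes of expedited regulatory reporting". Protocol 8.3.1 repeats this for IND safety reports and relies on the Investigator's classification. Protocol 11.4.6 and SAP 4.4.2 tabulate adverse events by the same three categories.

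**The concern.** The two sections give different answers for an event that has two reasonable causes, and this trial is likely to produce such events. Protocol 1.3 says corticosteroid therapy "is associated with ocular side effects, in particular cataract and corticosteroid-induced increased intraocular pressure (IOP"). Protocol 1.2 attributes vision loss in uveitis to complications of the disease, "due to cystoid macular edema, glaucoma, retinal detachment, subretinal fibrosis, cataract, and optic disk atrophy". Cataract therefore has both a steroid cause and a disease cause in the protocol's own background text, and glaucoma or raised IOP comes close to the same position. Other steroids add a further candidate cause: existing systemic or topical treatment may be tapered over 3 months after Day 1 (Protocol 7.2), and recurrences may be treated with local steroids (Protocol 7.6).

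Two outputs are at stake. The first is the count of related events in the tables by relationship. That count matters more here because sham subjects were discontinued and all subjects unmasked (Protocol 3.1). Later follow-up has no concurrent control, so the Investigator's attribution is one of the few causal indications left. The second is the expedited-reporting trigger, which takes the Investigator's category as its input.

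**Working it through.** No arithmetic applies, and the plan gives no figure to reproduce. The check is to apply both sections to the four combinations of a reasonable link to the implant, device or procedure and a reasonable alternative cause.

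| Reasonable treatment link | Reasonable alternative cause | Protocol 8.1 | Protocol 8.1.5 |
|---|---|---|---|
| Yes | No | Associated | *Possibly* or *Probably Related* |
| Yes | Yes | Associated | *Not Related* only |
| No | Yes | Not associated | *Not Related* |
| No | No | Not associated | *Not Related*, where the evidence shows no plausible link |

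The second row is the conflict:

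1. The event meets *Not Related*, because the alternative-cause limb is joined by *or* and so suffices alone.
2. It fails *Possibly Related*, because another condition does reasonably support the event.
3. It fails *Probably Related*, because another cause has not been excluded.
4. It is nevertheless associated under 8.1, because a reasonable possibility of causation is all that section asks for.

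If the last clause of *Possibly Related* were read as an alternative and not as a condition, the event would satisfy two categories at once. The scale would still give no single answer.

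Next, the downstream uses:

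- **Tables by relationship (Protocol 11.4.6, SAP 4.4.2).** A second-row event appears under *Not Related*. It is present in the table, but not among the related events.
- **Expedited reporting (Protocol 8.1.5, 8.3.1).** A 15-day report needs three things together: the event is associated (*possibly* or *probably* related in the Investigator's classification), serious and unexpected. A second-row event fails the first. The category changes the outcome only when the other two hold.
- **Expectedness (Protocol 8.1).** The sponsor judges this against the Investigator's Brochure. Neither 8.1 nor 8.3.1 describes a separate causality assessment by the sponsor that could override the Investigator's category.
- **SAE reporting to the sponsor (Protocol 8.3.1).** All SAEs go to the sponsor within 24 hours, whatever the relationship. The case arrives, but its category is not corrected.

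**The case against.** The strongest case on the other side is that only a label is at risk. All TEAEs are tabulated by system organ class and preferred term. IOP elevation, treatment for raised IOP, cataract development or worsening, and cataract procedures are safety endpoints in their own right (SAP 1.1). IOP and slit-lamp findings are summarised by visit (SAP 4.4.4, 4.4.5). SAEs reach the sponsor regardless of cause. The trial was stopped early and the SAP is descriptive only. All of this stands, and it limits the consequence without removing the conflict.

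Three stronger readings are tempting, and the documents do not support them:

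- **Any conceivable second cause forces *Not Related*.** The limb requires a reasonable causal relationship, which the Investigator must judge event by event. A list of uveitis complications does not settle that judgement. For IOP in particular, Protocol 1.2 names glaucoma and not raised pressure, and exclusions 13 and 14 in Protocol 4.2 remove most subjects with glaucoma, ocular hypertension or IOP above 21 mmHg at Screening (the Synopsis is looser). Cataract may have been removed before enrolment (Protocol 7.4).
- **Cataract and IOP events would be kept out of expedited reporting.** That depends on the Investigator's Brochure, which is not among the documents. If the brochure lists them, they are expected and would not be expedited under any category, unless severity or frequency exceeded what it describes.
- **The events vanish from the relationship tables.** Those tables show all three categories, including *Not Related*.

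**Conclusion.** The conflict between Protocol 8.1 and 8.1.5 holds on the wording alone. An event with both a reasonable treatment link and a reasonable alternative cause is associated under one section and can only be *Not Related* under the other.

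The surer consequence is under-counting of related events in the tables by relationship, if sites follow 8.1.5 as written. The second is narrower: a serious, unexpected event with a competing cause may not be expedited. Retinal detachment needing surgery, or severe intraocular inflammation, could be such events if the brochure does not cover them; Protocol 8.1.3 can make either an SAE.

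The documents do not allow the number of affected events to be estimated. It depends on how many adverse events have two reasonable causes and on how literally Investigators apply the scale. Efficacy summaries, all-causality TEAE tables and 24-hour SAE reporting do not change.

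**What to change.** Align 8.1.5 with 8.1 by two deletions:

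- From *Not Related*, remove the limb "there is a reasonable causal relationship between non-investigational product, concurrent disease, or circumstance and the AE". The limbs on absence of a plausible relationship and on biological implausibility remain.
- From *Possibly Related*, remove "the AE is not reasonably supported by other conditions". The category then means that a reasonable possibility exists, even if other causes are also reasonable.

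It would also help to state whether the sponsor makes its own causality assessment for expedited reporting.

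If codings are re-queried before database lock, the query should cover ocular adverse events and all SAEs, in every relationship category and both arms, with identical wording. Querying only events coded *Not Related* could move codings in one direction only. Keep the original assessment and report both. If there is no re-query, the study report should disclose the limitation of the scale.

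The cost is two edited definitions and, if chosen, one round of queries in a stopped trial planned for about 60 subjects. The downside is that more events will be shown as related, and any re-query would be done with treatment known.

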8.2 Recording of Adverse Events

Medical conditions or diseases present before a subject starts study treatment are only considered AEs if they worsen after the start of the study treatment.

Adverse events may be spontaneously reported or elicited at each study visit through open-ended questioning, examination, or evaluation of a subject. To prevent reporting bias, subjects should not be questioned regarding the specific occurrence of one or more AEs.

The Investigator will record all AEs in the eCRF. Where a diagnosis is possible, it is preferable to report the diagnosis rather than a series of terms (signs/symptoms) relating to the diagnosis. If a definitive diagnosis is not possible, the individual symptoms and signs should be recorded.

The following information must be captured for all AEs:

- onset and end date
- severity
- seriousness
- relationship to study treatment or the injection device, procedure
- action taken

- any treatment required
- outcome

If treatment for the AE was administered, it should be recorded on the appropriate concomitant medication/procedure eCRF page. Each distinct AE should be recorded separately.

